### **Exclusion criteria**

- Use of sacubitril/valsartan by patients with prior angioedema history is contraindicated; patients with a recorded angioedema diagnosis prior to index date (see [Section 7.2.5](#) for definition of ‘index date’) are excluded from all cohorts.
- Patients with concurrent prescriptions or pharmacy fills for sacubitril/valsartan and ACEI (i.e., prescription/pharmacy fill on the same day) will also be excluded and will be reported to reflect violation of the 36-hour washout period of ACEI prior to initiation of sacubitril/valsartan.
- For the assessment of ‘hepatotoxicity’, we will exclude patients with a hepatotoxic event prior to index date (chronic, acute, viral [including HIV], alcohol- or drug-induced, or codes without defined cause [e.g., “hepatitis unspecified”]. Patients with codes indicating hepatic morbidity suggestive of another etiology [“other specified disorders of liver”, biliary or alcohol-induced hepatotoxicity]) before or up to 7 days after the index date will be excluded. This will account for late determination or recording thereof of the excluded etiology of the event.
- Patients with a recorded history of chronic renal disease will be excluded for the assessment of ‘renal impairment’.

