### 6.1 Primary objective

1. To estimate the incidence of specific safety events of interest in HF patients newly starting treatment with sacubitril/valsartan (regardless of prior use of ACEIs or ARBs)

The primary safety event of interest is:

- Angioedema

Secondary events of interest are:

- Hypotension
- Hyperkalemia
- Hepatotoxicity
- Renal impairment

2. To estimate the incidence of all specific safety events (as mentioned above) in HF patients newly starting treatment with sacubitril/valsartan without prior exposure to ACEIs or ARBs

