#### 7.1.1 Rationale for study design

To obtain a robust estimate of the incidence of angioedema – the primary safety event of interest – as well as of the other safety events (i.e. hypotension, hyperkalemia, hepatotoxicity, and renal impairment) in patients newly starting sacubitril/valsartan (incident users), an initial cohort of all sacubitril/valsartan initiators will be identified (regardless of prior exposure to ACEIs or ARBs) with patient accrual beginning at the specific launch date of sacubitril/valsartan (see [Table 7-1](#)) in those EU countries from which healthcare database information will be used for this study (see [Section 7.4](#) ‘Data sources’). In addition, an initial contemporaneous comparator cohort of ACEIs initiators will be identified. Data collection will end when the necessary sample size of 24,000 PYs is reached (see [Section 7.5](#) ‘Study size/power calculation’), but on 31 December 2021 at the latest (even when the target sample size is not reached).

A new user design ([Ray 2003](#), [Food and Drug Administration 2013](#), [Yoshida et al 2015](#)) is proposed to minimize the risk of a prevalent user bias and depletion of susceptibles. This is of particular importance for ACEIs users. Sacubitril/valsartan was newly introduced to the market and the cohort of users therefore automatically consists of new users. As indicated in the sacubitril/valsartan ‘Summary of Product Characteristics’ (SmPC), it is contraindicated for patients with a known history of angioedema related to previous ACEI or ARB therapy, or with hereditary or idiopathic angioedema. The combination of sacubitril/valsartan with an ACEI is contraindicated due to the increased risk of angioedema. Sacubitril/valsartan must not be initiated within 36 hours after taking the last dose of ACEI therapy.

Since the majority of sacubitril/valsartan users are expected to have been treated with an ACEI or ARB before starting sacubitril/valsartan, these patients will likely have a lower baseline risk of angioedema as susceptible patients have been depleted. ACEI initiators who are treatment

naïve to ACEIs and ARBs however, will likely have a higher baseline risk of angioedema since this population includes all patients who are susceptible to an angioedema event.

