### **7.2.6 Follow-up**

Eligible patients will be followed from their cohort entry until the occurrence of the outcome of interest, death, the last date of follow-up available in the data set, or the study end date.

Patients will be censored in the respective cohort if they:

- Had stopped their treatment with sacubitril/valsartan or ACEI
- Added treatment with another renin-angiotensin-aldosterone system (RAAS blocking agent (i.e., add-on of an ACEI [only for initiators of sacubitril/valsartan], an ARB, or aliskiren)

- Switched initial treatment to another RAAS blocking agent (i.e., sacubitril/valsartan to an ACEI, ARB or aliskiren; ACEI to sacubitril/valsartan, an ARB, or aliskiren [switching within the ACEI class, however, was not censored])
- Stopped contributing data to the database (e.g., patient died, or left the practice/health insurance, etc.), whichever will occur first.

See [Section 7.3.1](#) for detailed definitions regarding discontinuation, add-on, or switching.

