#### 7.7.1.2.1 Demographic and baseline characteristics of exposure cohorts

Demographic and baseline clinical characteristics of adult patients with HF initiating sacubitril/valsartan or ACEIs will be described, using contingency tables for categorical variables and mean, standard deviation (SD), range, median and interquartile range (IQR) for continuous variables in each database. Differences in demographic and baseline characteristics of adult patients with HF initiating either sacubitril/valsartan or using an ACEI will be assessed via standardized mean differences (SMD). A cross tabulation of age groups and sex will be provided for adult patients with HF initiating either sacubitril/valsartan or using an ACEI.

Information on cohort attrition will be provided in a study diagram and table. Treatment-related information (e.g. treatment duration, reason for discontinuation, switch/add-on therapy, etc.) will be summarized per treatment cohort.

In this context, we also aim at investigating the 36-hour washout period recommended in the SmPC of sacubitril/valsartan for patients previously using ACEI who started on sacubitril/valsartan in actual clinical care setting as requested by the PRAC. The current proposal is to assess the proportion of adult patients with HF initiating sacubitril/valsartan for whom there is evidence indicating concurrent use during the 36-hour period. This will be performed by assessing the proportion of sacubitril/valsartan users with concurrent prescriptions (or pharmacy fills) of ACEI (i.e. on the same day). Concurrent prescriptions (or pharmacy fills) are the only reliable indicator of non-adherence to the 36-hour washout period (see also [Section 7.10](#)).

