### 7.9 Limitations of the research methods

The most important uncertainty is the use of sacubitril/valsartan, which may decrease the precision of the estimates from the study. We expect major issues with the number and selection of the sacubitril/valsartan and ACEI cohorts that are naïve to prior ACEI/ARB exposure. Difference between cohorts will be inspected by covariates (baseline characteristics) and a propensity score.

The limitations of this study will be mainly due to the availability and level of detail of data. Not all potential confounders (e.g. life style factors such as smoking, BMI) are contained in the databases, and not all variables contain the information in desired detail. We will be missing

information on race – which is an important risk factor and effect modifier for angioedema – in most databases. However, we will use available information on race (e.g. from CPRD) in a sensitivity analysis. Particularly, information on the prescribed dose and duration of a prescription is not contained in all databases and has to be estimated, which might lead to misclassification of exposure. None of the databases have data on actual drug intake. This implies that we do not know whether the patient actually took the drug. Assessment of the 36-hour washout period is therefore limited to determining concurrent prescriptions (or pharmacy fills) of ACEI and sacubitril/valsartan on the same day. As angioedema risk is higher if sacubitril/valsartan is started before the determined washout period from ACEI, the risk of angioedema in cohort 1 may be slightly overestimated.

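### Starters with a same-day ACEI record are excluded and only counted: the cohort 1 angioedema rate leaves out their events, and section 7.9 does not mention that downward effect

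*Protocol*

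**What the plan says.** **Target.** Primary objective 1 (section 6.1) is incidence "in HF patients newly starting treatment with sacubitril/valsartan (regardless of prior use of ACEIs or ARBs"). Section 7.1.1 says "an initial cohort of all sacubitril/valsartan initiators will be identified (regardless of prior exposure to ACEIs or ARBs"). The Abstract, under Population, adds in parentheses that sacubitril/valsartan and an ACEI are not used together.

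**Exclusion.** Section 7.2.4 first removes patients with earlier angioedema, who "are excluded from all cohorts". The next bullet reads: "Patients with concurrent prescriptions or pharmacy fills for sacubitril/valsartan and ACEI (i.e., prescription/pharmacy fill on the same day) will also be excluded". It adds that these patients "will be reported to reflect violation of the 36-hour washout period of ACEI prior to initiation of sacubitril/valsartan". Table 3-1 shows that this criterion came in with Amendment 1.

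**What is reported about them.** Section 7.7.1.2.1 proposes "assessing the proportion of sacubitril/valsartan users with concurrent prescriptions (or pharmacy fills) of ACEI (i.e. on the same day"), and section 7.10 commits to reporting same-day prescriptions as washout violations. None of these places plans an event count, person-time or rate for the group.

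**Risk.** Section 7.1.1 says that combining the two drugs raises angioedema risk. Section 7.7.1.2.1 treats same-day records as the one dependable sign that the washout was not observed.

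**Bias.** Section 7.9 says that, because early starting raises risk, "the risk of angioedema in cohort 1 may be slightly overestimated".

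**Later ACEI use.** Section 7.2.6 censors on "add-on of an ACEI [only for initiators of sacubitril/valsartan], an ARB, or aliskiren". The note in section 7.3.1.2 places patients who change from an ACEI to sacubitril/valsartan in both the ACEI and the sacubitril/valsartan cohorts.

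**The concern.** The study exists to give a real-world angioedema rate for sacubitril/valsartan, and the PRAC asked for the washout to be looked at in routine care. The one group in which a washout violation can be seen, and which the protocol itself expects to be at higher risk of the primary event, leaves the cohort and reappears only as a number or proportion. Any angioedema in that group enters neither the primary rate nor the washout report. A reader of section 7.9 would learn of an upward influence on the cohort 1 rate and would not be told that a downward one has been built in.

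The second issue is timing. The angioedema and hepatotoxicity bullets in section 7.2.4 are tied to the index date; the same-day bullet is not. If a later same-day pair counts, patients are selected on information that arises after follow-up has begun.

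**Working it through.** **1. The plan's own figure.** Section 7.5 expects 132 cases in 24,000 patient-years (PY). The rate is 132/24,000 = 5.50 per 1,000 PY. Exact Poisson limits are χ²(0.025; 264)/(2 × 24,000) = 4.60 and χ²(0.975; 266)/(2 × 24,000) = 6.52 per 1,000 PY. This agrees with the stated 4.6 to 6.5.

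**2. Direction of the exclusion.** Let R be the rate in the retained starters, p the share of all starters' person-time that same-day starters would contribute if kept, and k their rate divided by R. Then

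rate in all starters = R(1 − p) + p·k·R = R[1 + p(k − 1)].

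For any p > 0 and k > 1 this exceeds R. The sign follows from the protocol's statement that the combination raises risk. The size needs p and k, and the documents give neither.

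**3. What it would take to matter.** To move 5.5 beyond the planned upper limit of 6.5, p(k − 1) must exceed 6.5/5.5 − 1 = 0.18. This is a threshold, not an estimate.

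Section 5.1 gives a fourth-interim rate of 0.7 per 1,000 PY. At that rate, 24,000 PY would yield 0.7 × 24 = 16.8 events, so one further event would raise the count by 1/16.8, about 6%. The text does not say whether that interim rate was computed with this exclusion in force.

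**4. Why section 7.9 and step 2 can both be right.** Take assumed values purely to show the signs: 5% same-day violators, 5% undetected violators, both with three times the rate of washout-adherent starters (set to 1).

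- Observed after exclusion: (0.90 × 1 + 0.05 × 3)/0.95 = 1.05/0.95 = 1.105
- All starters: 0.90 × 1 + 0.10 × 3 = 1.20
- Observed relative to adherent use: 1.105, so too high
- Observed relative to all starters: 1.105/1.20 = 0.921, so too low

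The direction depends on the reference. Section 7.9 gives one direction and names no reference.

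**5. Timing and scope, side by side.**

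| Situation | Section 7.2.4 read literally | Other sections |
|---|---|---|
| Both drugs recorded on the sacubitril/valsartan index date | Excluded | Taken literally, 7.2.6 could also count the ACEI record as an add-on and censor at once |
| Same-day pair later in sacubitril/valsartan follow-up | Could be excluded, with all earlier person-time | 7.2.6: censor, earlier time kept |
| ACEI user whose change to sacubitril/valsartan falls on an ACEI fill date | Could lose earlier ACEI time as well | 7.3.1.2: counted in both cohorts |

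That the exclusion covers every cohort is an inference: the bullet follows one that names all cohorts, is linked to it by the word also, and carries no restriction of its own.

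**The case against.** **The population is defined without concomitant use.** This stands. The Abstract says so, the objective's wording concerns prior rather than concurrent ACEI use, and excluding dual exposure fits the on-treatment logic of section 7.2.6. A reader might infer that the exclusion contradicts the primary objective; the documents do not support that. What remains is that the resulting rate applies to a narrower group than all real-world starters and should be labelled so.

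**Section 7.9 is right on its own terms.** A reader might infer that it states the wrong direction of bias. Read in order, it says that intake is unknown, that only same-day records can be checked, and then that the rate may be slightly high. That describes violators who were not detected and remain in the cohort. Relative to washout-adherent use it is correct, and it is hedged. It is incomplete, not wrong.

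**The exclusion concerns initiation.** Section 7.2.4 refers to the washout before starting, and section 7.7.1.2.1 frames the check around initiators, so removal for a later same-day pair is only one reading. Figure 7-2, which is not available in the text reviewed, may settle it. The bullet still lacks the explicit anchor that its neighbours have.

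**The size is unknown.** A reader might put assumed shares and risk ratios into the formula and quote a percentage understatement. That figure would rest wholly on the assumptions. It would also overlook that, under section 7.2.6, a retained same-day starter might be censored almost at once and contribute little person-time.

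**The PRAC commitment is met as written.** Nothing in the protocol shows that the PRAC asked for an event rate in violators. Reporting one is an improvement, not an unmet obligation.

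**Conclusion.** The point holds in a limited form and is worth acting on. The cohort 1 angioedema rate applies to starters without a same-day ACEI record. If same-day starters have the higher risk stated in section 7.1.1, it lies below the rate in all real-world starters by an amount that the documents do not allow to be estimated and that may be small. Their events are planned to appear nowhere, although the patients will already have been identified. Section 7.9 covers only the upward effect of undetected violators. The exclusion's timing and scope are not explicit, and on a literal reading they conflict with sections 7.2.6 and 7.3.1.2. The conclusion rests on the protocol's own statement of raised risk and, for scope, on reading the bullet as applying to all cohorts.

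**What to change.** 1. In section 7.2.4, limit the exclusion to same-day records on the sacubitril/valsartan index date and to the sacubitril/valsartan cohorts. Keep ACEI-cohort time before a switch, and handle later ACEI records by the existing censoring rule in section 7.2.6.
2. Report angioedema events, person-years and an exact incidence rate for the excluded group, beside the proportion already planned.
3. Add a sensitivity analysis of the cohort 1 rate that includes these patients, stating that the ACEI record on the index date does not itself trigger censoring. Without that rule they would contribute almost no follow-up.
4. Amend section 7.9 to give both directions with their references: undetected violators raise the rate relative to washout-adherent use, while excluding identified same-day starters lowers it relative to all starters.

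The cost is a few table rows and one sensitivity run on patients already identified. The drawback is that the rate in the excluded group will be imprecise. The changes concern the analysis only and leave the clinical washout rule untouched.

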### **7.2.5 Cohort start**

The date of the first recorded prescription (or pharmacy fill) for sacubitril/valsartan or ACEI in the study period will be defined as the cohort entry (= start of follow-up or ‘index date’). A minimal look-back period of 365 days is used to determine baseline characteristics.

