Accruing the required sample size for the comparison of patients initiating sacubitril/valsartan treatment without prior ACEI/ARB use with those newly initiating treatment with ACEIs/ARBs within the proposed timelines will be very unlikely. It should be expected that many HF patients (both prevalent and incident) will have been previously exposed to an ACEI used as treatment for hypertension or other comorbid diseases prevalent in HF patients (e.g., acute myocardial infarction, diabetic nephropathy). A US study in patients with incident HF diagnosed between 2005 and 2008 from four sites participating in the Cardiovascular Research Network (CVRN) found an exposure prevalence to ACEIs or ARBs in patients with incident HFrEF (n=3,941, mean age 69 years) of 43% ([Goldberg et al 2013](#)). In the European ‘ESC-HF Long-Term Registry’ a prospective cohort study with primary data collection, including over 7,400 patients with prevalent chronic HF (median age 66 years) were enrolled over two years. In the subgroup of patients with HFrEF (n=4,792), 92.2% were treated with ACEIs or ARBs at baseline ([Maggioni et al 2013](#)). Thus, indicating that the absolute number of ACEI initiators who are treatment naïve to ACEIs and ARBs will be limited. If necessary, it was initially planned to supplement the contemporaneous comparator cohort with a historical cohort of ACEI initiators who are treatment naïve to ACEIs using data prior to Entresto® market approval if needed. However, the most recent interim report for the LCZ696B2014 study identified a total of 116,041 ACEI initiators being treatment naïve to ACEIs/ARBs [REDACTED] when both ARS and GePaRD were included. Based on these results, inclusion of a historical cohort of ACEI initiators treatment naïve to ACEIs/ARBs does not seem necessary.

In addition, to explore the impact of depletion of susceptibles we will assess the rate of events in users of ACEIs with prior use of ACEIs/ARBs.

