### 7.2.4 Inclusion and exclusion criteria

#### Inclusion criteria

Patients will be required to:

- Have initiated sacubitril/valsartan or using an ACEI during the study period
- Be aged  $\geq 18$  years at the time of the first prescription (or pharmacy fill) for sacubitril/valsartan or an ACEI. If the exact date of birth is not known, January 1st of the calendar year the patient turns 18 years will be the start date when only the year is known, and the first date of the month when the month and the year are known
- Have a recorded diagnosis of HF in the database prior to or within three months (90 days) after the first prescription (or pharmacy fill) of sacubitril/valsartan or ACEI in the study period

- Have  $\geq 365$  days of valid database history prior to the first prescription (or pharmacy fill) for sacubitril/valsartan or an ACEI (i.e., the patient was registered in the database for at least one year)

*Note:* In GePaRD, only confirmed diagnoses of HF will be selected by using the following algorithm based on records with a confirmed diagnosis status:

- At least one primary hospital discharge diagnosis of HF
- OR at least two outpatient HF diagnoses

In all cases, the first recorded claims date in the context of a HF diagnosis will be considered as the diagnosis date. In all other databases one diagnosis of HF from in- and/or outpatient registry data or electronic medical records will be used.

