### 7.3.1.2 ACEI user cohorts

- ACEIs – users regardless of prior ACEI/ARB use (cohort 3)

[figure not shown]
This group includes all patients fulfilling the inclusion criteria ([Section 7.2.4](#)) and using ACEIs during the study period – regardless of prior exposure to ACEIs or ARBs. This cohort will be a mix of prevalent and incident ACEI users.

- ACEIs – without prior use of ACEI/ARB - treatment-naïve (cohort 4)

Cohort 4 is the subset of patients from cohort 3. It includes patients who did not use ACEIs/ARBs in the 365 days prior to index date. This sub-cohort corresponds to new ACEIs users - naïve to ACEIs/ARBs.

Note: Patients can be included in more than one cohort. Patients changing from ACEI to sacubitril/valsartan will be included in the corresponding ACEI cohort, as well as the sacubitril/valsartan cohort (only the first change will be considered). Patients changing from sacubitril/valsartan to an ACEI, however, will be censored. [Figure 7-2](#) illustrates cohort allocation and start of follow-up based on various exposure scenarios for sacubitril/valsartan and ACEI users.

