**Figure 7-2 Cohort allocation based on various exposure scenarios for sacubitril/valsartan and ACEI users**

sac/val = sacubitril/valsartan; ACEI = angiotensin converting enzyme inhibitor; ARB = angiotensin receptor blocker; index date = date of first prescription or pharmacy fill of sacubitril/valsartan (cohort 1 & 2) or ACEI use (cohort 3 & 4) (not shown for the excluded patients); HF = heart failure (diagnosis must be recorded at any time prior or within 3 months after index date)

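### ACEI users whose heart failure is recorded more than 90 days after their first in-period ACEI prescription can never enter cohort 3, yet enter cohort 1 if they later start sacubitril/valsartan

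*Protocol*

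**What the plan says.** Protocol section 7.2.5 (Cohort start) states that the date of the "first recorded prescription (or pharmacy fill) for sacubitril/valsartan or ACEI in the study period will be defined as the cohort entry". Section 7.2.3 opens the study period at the national launch date, which Table 7-1 puts between December 2015 and October 2016.

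The inclusion criteria in 7.2.4 require a recorded HF diagnosis "prior to or within three months (90 days) after the first prescription (or pharmacy fill) of sacubitril/valsartan or ACEI in the study period". The 365 days of database history are tested at the first prescription as well.

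The legend of Figure 7-2 repeats both rules. The index date is the "date of first prescription or pharmacy fill of sacubitril/valsartan (cohort 1 & 2) or ACEI use (cohort 3 & 4", and the HF "diagnosis must be recorded at any time prior or within 3 months after index date". The index is thus specific to the drug, but there is only one per drug.

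Three other statements bear on this:

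- The Population paragraph of the abstract describes patients with prevalent or incident HF.
- Section 7.3.1.2 says of cohort 3: "This cohort will be a mix of prevalent and incident ACEI users". Its closing note places patients who move from an ACEI to sacubitril/valsartan in both the ACEI and the sacubitril/valsartan cohort.
- Section 7.1.1 expects that "many HF patients (both prevalent and incident) will have been previously exposed to an ACEI used as treatment for hypertension".

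**The concern.** The same entry sentence works differently in the two arms. Sacubitril/valsartan is new at launch, so its first in-period prescription is a true start and HF has normally been diagnosed by then. For a patient on a long-running ACEI, the first in-period prescription is simply the first refill after launch. It marks no clinical event, yet it sets a deadline for the HF diagnosis.

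A patient treated with an ACEI for hypertension who develops HF two years into the study is an HF patient on an ACEI from then on, but belongs to no ACEI cohort. Section 7.1.1 expects ACEI use before HF to be common. At stake are the cohort 3 incidence rates (secondary objective 2) and the comparison of cohort 1 with cohort 3 (exploratory objective 3 in 6.3, comparison c in 7.7.1.2.2). Table 7-2 ticks a different cohort for that objective; this is a separate inconsistency, and 6.3 and 7.7.1.2.2 are followed here.

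**Working it through.** The protocol gives no figure for the patients affected, so the check applies its rules to patient timelines.

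**Rules as written.** Count days from launch. Let i be the first ACEI prescription on or after day 0, s the first sacubitril/valsartan prescription, and h the day HF is recorded.

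- Cohort 3: h ≤ i + 90. Cohort 4: also no ACEI/ARB in the 365 days before i.
- Cohort 1: h ≤ s + 90. Cohort 2: also no ACEI/ARB in the 365 days before s.

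**Timelines.** Continuous use means a fill every 30 days from day −400. The first in-period fill is then day 20, and the HF deadline is day 20 + 90 = 110.

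| Patient | ACEI | HF day | Sacubitril/valsartan | Cohorts entered |
|---|---|---|---|---|
| A | continuous | 700 | day 900 | 1 only |
| B | continuous | 700 | none | none |
| C | continuous | −100 | day 900 | 1 and 3 |
| D | days 0–60, restart day 720 | 700 | none | none |
| E | days 0–60 | 700 | day 720 | 1 and 2 |
| F | first on day 710 | 700 | none | 3 and 4 |
| G | continuous | 60 | none | 3 |

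A and C differ only in when HF was recorded. Both switch drug, but only C is in both cohorts as 7.3.1.2 says. D has gone 720 − 60 = 660 days since the last ACEI fill and meets the 365-day naïve definition at the restart, but is shut out because i = 0 and h = 700 > 90. E has the same history, receives sacubitril/valsartan instead, and enters cohorts 1 and 2.

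**Share of the study period closed to such patients.** For someone whose first in-period fill falls at launch, HF recorded after day 90 cannot qualify. With 30.4375 days per month, the share is (D − 90)/D:

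- Cut at 31 December 2019 (primary analysis): Spain, 39 months, D = 1,187, 92.4%; Denmark and UK, 49 months, D = 1,491, 94.0%.
- Full period: Germany, 48 months, D = 1,461, 93.8%; longest databases, 61 months, D = 1,857, 95.2%.

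These are shares of calendar time, not of patients.

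**Illustrative effect on the cohort 3 rate (inputs assumed).** Let x be the excluded person-time as a fraction of cohort 3 person-time, and r the angioedema rate in the excluded relative to cohort 3 as built. The ratio of the cohort 3 rate as built to the rate with these patients included is (1 + x)/(1 + x·r).

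- r = 0.8, x = 0.1: 1.1/1.08 = 1.02.
- r = 0.3, x = 0.5: 1.5/1.15 = 1.30.
- r = 1.25, x = 0.1: 1.1/1.125 = 0.98; x = 0.5: 1.5/1.625 = 0.92.

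The effect can go either way. Long-term tolerant users would have a low rate, but 5.1.2 notes that HF may itself raise angioedema risk, so patients soon after an HF diagnosis need not be at low risk.

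**The case against.** The strongest reply is that little of importance depends on this. The primary objectives concern cohorts 1 and 2, whose index date works as intended, and the 24,000 patient-year target is untouched. Section 6.3 labels every comparison exploratory because of how the ACEI comparator is selected, and 7.9 warns of bias with any ACEI comparator. The note in 7.3.1.2 could also be read as covering only switchers who met the inclusion criteria, and the scenarios drawn in Figure 7-2 are not visible here. Most of this stands and limits the severity. It does not remove the point: the cohort 3 rates are a secondary objective, 7.9 discusses depletion of susceptibles and channelling but not this mechanism, and the figure's legend repeats the rule.

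A reader might infer more than the documents support:

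- *The comparator is not concurrent.* Section 7.1.1 says that "an initial contemporaneous comparator cohort of ACEIs initiators will be identified". That concerns initiators, and the contrast drawn there is with a historical, pre-approval cohort. Early entry of prevalent users into cohort 3 does not contradict it.
- *Some 43% of incident HF patients are barred.* That figure in 7.1.1 is ACEI or ARB exposure in a US study of incident HF diagnosed 2005–2008. It does not show how many had a first in-period ACEI fill more than 90 days before HF.
- *Some 80% of cohort 3 enters at launch.* The interim counts give (567 − 116)/567 = 79.5% non-naïve. These patients are already included, and they may be prior ARB users starting an ACEI at any date.
- *Calendar period is missing from the propensity score.* Section 7.3.3 lists characteristics to summarize, and 7.7.1.2.2 leaves the score's details to the SAP.

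**Conclusion.** The point holds in a limited form. As written, 7.2.4 and 7.2.5 exclude from cohort 3 every continuing ACEI user whose HF is recorded more than 90 days after the first in-period fill. Those who later start sacubitril/valsartan enter cohort 1, so for them the rule conflicts with the switcher note in 7.3.1.2. It also falls short of the abstract's population of prevalent or incident HF. Only that subset moves across; it would be wrong to say that all the excluded patients reappear in cohort 1. Cohort 4 loses only restarters such as patient D, since continuing users are non-naïve by design.

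The size is unknown. The rate ratios above (0.92 to 1.30) rest wholly on assumed inputs, and the direction is uncertain. The primary rates are unaffected and the comparisons are exploratory. This should be fixed before the final analysis, but it does not put the study's main result in doubt.

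**What to change.** Amend 7.2.5 so that the ACEI index is set in two steps:

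1. A patient who qualifies at the first in-period ACEI prescription keeps that index and the 90-day HF allowance.
2. A patient who does not qualify is indexed at the first later in-period ACEI prescription on or after the date when recorded HF, 365 days of history and age are all satisfied.

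Assess cohort 4 status at that index, or at the first later ACEI start with no ACEI/ARB in the preceding 365 days. State that the index may differ between cohorts 3 and 4, and recheck the exclusion criteria at the index used. Reconcile 7.2.4, 7.3.1.2 and the Figure 7-2 legend.

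Do not re-index every ACEI user at or after HF. That would remove the 90-day allowance from the ACEI arm only. A naïve starter with HF recorded 30 days later would move to the next fill, lose naïve status, and lose the early weeks in which 5.1.2 places about half of angioedema cases.

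The cost is one paragraph, one step in the shared SAS program and its R counterpart, and ACEI counts that no longer match the interim reports. No new data source is needed, provided the local extracts were not already cut to patients meeting the present rule. Adding calendar period of index to the propensity score is at most a suggestion for the SAP.
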